18.0 DATA AND SAFETY MONITORING

This trial will be monitored in accordance with the NCI approved University of Michigan Comprehensive Cancer Center Data and Safety Monitoring Plan.

The study specific Data and Safety Monitoring Committee (DSMC), consisting of the protocol investigators, data manager or designee and other members of the study team involved with the conduct of the trial, will meet quarterly or more frequently depending on the activity of the protocol to provide continuous review of the data and patient safety. The discussion will include matters related to the safety of study participants (SAE/UaP reporting), validity and integrity of the data, enrollment rate relative to expectations, characteristics of participants, retention of participants, adherence to the protocol (potential or real protocol deviations) and data completeness.

At the regular DSMC meetings, the protocol specific Data and Safety Monitoring Report form will be completed. The report will be signed by the Principal Investigator or by one of the co-investigators.

Data and Safety Monitoring Reports will be submitted to the University of Michigan Comprehensive Cancer Center Data and Safety Monitoring Board (DSMB) on a quarterly basis for independent review.

19.0 QUALITY ASSURANCE AND AUDITS

The Quality Assurance Review Committee (QARC) of The University of Michigan Comprehensive Cancer Center (UMCCC) performs quality assurance audits of investigator-initiated clinical trials. Audits provide assurance that trials are conducted in compliance with the protocol. Further, they ensure that study data are collected, documented and reported in compliance with Good Clinical Practices (GCP) Guidelines and regulatory requirements.

A QARC audit of each clinical trial is conducted annually. Audits occur within the month of the study's initial IRB approval (provided the trial is open, and study accrual is greater than two subjects).

All audit findings are reported by QARC to the UMCCC Data and Safety Monitoring Board. These findings are followed-up by the DSMB until they have been resolved. The DSMB can also request QARC for a 'for cause' audit of the trial if the board identifies a need for a more rigorous evaluation of study-related issues. A regulatory authority (e.g. FDA) may also wish to conduct an inspection of the study, during its conduct or even after its completion. If an inspection has been requested by a regulatory authority, the principal investigator must immediately inform the Clinical Trials Office that such a request has been made.

20.0 STATISTICAL CONSIDERATIONS

20.1 Study Design

This is a Phase II trial of seven weeks RT+cetuximab for head and neck cancer in patients with good prognoses to determine if this treatment will be at least as effective as, but less toxic than, standard therapy. A total of 43 patients will be enrolled in order to obtain 36 patients that complete radiation treatment and have both biopsies taken. Thus, both the clinical primary endpoints and scientific secondary endpoints can be analyzed, as EGFR tumor information is useful for determining potential mechanisms of resistance to cetuximab. Based on the experience of UMCC 9921 and UMCC 2-21, accrual is expected to average one patient per month. To be considered evaluable, a patient must complete the full course of radiation/cetuximab. If radiation and/or cetuximab was stopped or modified due to toxicity, the patient is still evaluable. Inevaluable patients will be replaced.

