7.5.2 Research Biopsies

Two research biopsies will be obtained. These research biopsies will be delivered directly to the Radiation Oncology research laboratory. The pre-treatment research biopsy (5-10 mm³) will be taken prior to therapy to assess baseline EGFR pathway activation. This pre-treatment biopsy will be performed for research purposes if a suitable clinical biopsy specimen is not available. A clinical specimen will be suitable if the biopsy was performed at UMHS within 30 days of consent. The second biopsy will be obtained 7 days (+/- 2 days) after the loading dose of cetuximab and will be examined for changes in EGFR pathway activation. Both biopsies will be performed in the clinic, under local anesthesia, by an otolaryngologist or oral surgeon who is a co-investigator of the study. The second biopsy will only be obtained if it can be done without general anesthesia.

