13.0 CRITERIA FOR DISCONTINUATION OF TREATMENT

Unacceptable adverse event(s), intercurrent illness which prevents further administration of treatment, patient preference, progressive disease, life threatening or other unacceptable drug-related toxicity, changes in the patient's condition that render the patient unacceptable for

further treatment in the judgment of the investigators.

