20.3 Analysis Plan

20.3.1 Primary Objectives

20.3.1.1 *To confirm that reducing treatment intensity in non-smoking patients with HPV-related oropharyngeal cancer does not significantly increase the proportion of patients whose tumors recur, compared to our previous experience in similar patients receiving standard-intensity chemo-RT.*

The primary index of recurrence will be the proportion of patients who have local recurrence, distant metastases or second primaries (secondary analyses will be performed on each of these endpoints individually) within two years of the end of treatment. In the primary analysis, *null* hypothesis that the proportion of patients who fail is *greater* than 0.20 will be tested using an exact binomial test (at significance level $\alpha=0.20$). The proportion of patients who recur will be calculated, with a 95% exact binomial confidence interval.

20.3.1.2 *To compare the toxicity in patients receiving reduced intensity treatment to similar patients treated with 7 weeks of chemotherapy concurrent with RT ("standard therapy") in UMCC 2-21.*

Dysphagia and mucositis are measured on continuous scales; there are both observer and patient reports. The null hypothesis of no difference in dysphagia and mucositis at three, twelve and twenty-four months posttreatment between the reduced-intensity therapy versus UMCC 2-21 will be tested ($\alpha=0.20$) in a repeated measures analysis of covariance. In addition, the statistical significance of the difference between the current trial and UMCC 2-21 in the proportions of patients experiencing clinically significant (NCI CTCAE Grade 3 or worse) toxicities will be assessed using Fisher's exact test

(a=0.20).

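### The primary recurrence test names no analysis set; under the only population rule given (20.1), a patient stopped for progression during treatment would be replaced and left out

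*Combined protocol and SAP*

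**What the plan says.** Section 20.1 sets the only population rule in the plan: "To be considered evaluable, a patient must complete the full course of radiation/cetuximab". It has one exception: "If radiation and/or cetuximab was stopped or modified due to toxicity, the patient is still evaluable". It then adds: "Inevaluable patients will be replaced".

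Section 13.0 gives reasons for stopping treatment that are not toxicity: "intercurrent illness which prevents further administration of treatment, patient preference, progressive disease".

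Section 20.3.1.1 defines the endpoint: "The primary index of recurrence will be the proportion of patients who have local recurrence, distant metastases or second primaries", with the window "within two years of the end of treatment". The null hypothesis is a failure proportion above 0.20, tested by an exact binomial test at a significance level of 0.20. The section names no analysis set.

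On numbers, 20.1 says "A total of 43 patients will be enrolled in order to obtain 36 patients that complete radiation treatment and have both biopsies taken", and links these patients to the analysis of both the clinical primary endpoints and the biopsy endpoints. Section 7.5.2 makes the second biopsy conditional: "The second biopsy will only be obtained if it can be done without general anesthesia". The stopping rule in 20.2 is indexed by the number of patients enrolled.

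**The concern.** A patient taken off treatment for progressive disease has not completed the course and has not stopped for toxicity. On the words of 20.1 that patient is inevaluable and is replaced. Nothing in 20.3.1.1 brings the patient back, and its window, anchored to the end of treatment, does not say how earlier progression is classed.

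Few failures mean success in this test. If on-treatment progression is a failure, leaving the patient out removes one event from the numerator and one patient from the denominator, which favours the experimental regimen. Patients who stop by preference, or for an illness that is not toxicity, are dropped by the same rule, and that could move the result either way. The same progressor could also count toward stopping accrual under 20.2 and yet be missing from the final test.

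Section 20.4.2.1 intends a success here to motivate a non-inferiority trial. A denominator chosen after outcomes are known would be hard to defend.

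**Working it through.** **Inputs.** Null rate 0.20 and alpha 0.20 (20.3.1.1). Planned enrolment 43, target 36 (20.1). Historical failure rate 2/32 = 0.0625, Table 1 boundaries and the enrolled denominator (20.2). Table 2 (20.4.1). The share x of failures that occur on treatment is not in the documents; 5% to 25% is an assumed range.

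**1. The plan's own figure.** Exact binomial recursion over the Table 1 looks (2/5, 3/10, 4/15, 5/20, 6/25, 7/30) gives stopping probabilities of 0.046, 0.594, 0.912, 0.992 and 0.9997 at true rates 0.06, 0.2, 0.3, 0.4 and 0.5. Table 2 prints 0.05, 0.59, 0.91, 0.99 and 0.99, so it is reproduced. The recurrence test has no stated power to reproduce.

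**2. The number analysed.** The 36 are completers with both biopsies, but evaluability requires only completion. The evaluable number is therefore not fixed. I take 36 to 43, which assumes that replacements fall within the 43; 20.1 does not say.

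**3. Cutoffs.** The test passes at the largest k with P(X ≤ k | n, 0.20) ≤ 0.20. The fifth column adds one uncounted failure to a result exactly at the cutoff. The last column is explained in step 5.

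| n | cutoff k | P(pass) at 0.20 | power at 0.0625 | one failure added | share x at which P(pass) = 0.20 |
|---|---|---|---|---|---|
| 36 | 4 | 0.127 | 0.928 | 5/37, p=0.222 | 12.4% |
| 37 | 4 | 0.112 | 0.921 | 5/38, p=0.2004 | 15.2% |
| 38 | 4 | 0.099 | 0.914 | 5/39, p=0.180 | 17.8% |
| 39 | 5 | 0.180 | 0.967 | 6/40, p=0.286 | 3.0% |
| 40 | 5 | 0.161 | 0.963 | 6/41, p=0.261 | 5.9% |
| 41 | 5 | 0.144 | 0.959 | 6/42, p=0.238 | 8.6% |
| 42 | 5 | 0.129 | 0.955 | 6/43, p=0.216 | 11.2% |
| 43 | 5 | 0.115 | 0.950 | 6/44, p=0.196 | 13.6% |

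One uncounted failure reverses a result at the cutoff for n = 36 and 39 to 42, and by a hair at 37. It does not at 38 or 43.

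**4. Expected cases.** Expected number = 43 × base rate × x; chance of at least one = 1 − (1 − base × x)^43.
- Base 2/32: 43 × 0.0625 × 0.05 = 0.13 and 43 × 0.0625 × 0.25 = 0.67; chance of at least one 0.13 to 0.49.
- Base 1/32: 43 × 0.03125 × 0.05 = 0.07 and 43 × 0.03125 × 0.25 = 0.34; chance 0.065 to 0.29.

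The lower base is shown because the two reference events appear to be one distant metastasis and one second primary (Sections 1.0 and 20.4.2.1), and a second primary is not progression that stops treatment. That these are the 2/32 of 20.2 is an inference.

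**5. Error rate at a true failure rate of 0.20.** If a share x of failures is excluded and replaced, the rate among evaluable patients is 0.2(1 − x)/(1 − 0.2x). At x = 12.4% this is 0.1752/0.9752 = 0.180, and P(X ≤ 4 | 36, 0.180) is 0.20. Solving for each n gives the last column: about 3% to 18%, ignoring early stopping.

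**6. With early stopping.** Apply Table 1 to all enrolled patients, with every failure known at once and counted. The probability of not stopping and then passing is as follows.

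| n | x = 10% | x = 25% |
|---|---|---|
| 36 | 0.157 | 0.228 |
| 38 | 0.130 | 0.198 |
| 39 | 0.202 | 0.275 |
| 40 | 0.186 | 0.261 |
| 43 | 0.143 | 0.218 |

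It reaches 0.20 at x of about 10% (n = 39), 13% (n = 40), 20% (n = 36), 22% (n = 43) and just over 25% (n = 38). Failures that become known late, and second primaries (which 20.2 does not count), would move these toward the values in step 5.

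**The case against.** The strongest reply is that three things must coincide: 20.1 must govern the recurrence test, which no sentence states; a patient must progress during a 7-week course in a good-prognosis group; and the final count must be borderline. Response imaging comes only 12 to 14 weeks after therapy (9.1), so few on-treatment progressions would be identified. The stopping rule watches enrolled patients, and 20.4.2.1 disclaims a definitive test. All of this stands, and it limits the size of the problem.

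The direction is also conditional. If progression before the end of treatment were kept in the denominator but not classed as recurrence, dropping the patient would raise the failure proportion. So the bias toward success holds only if such progression is a failure, which is what the plan leaves unsaid. The thresholds in steps 5 and 6 rest on an unsourced share applied to all failures, second primaries included, and show order of magnitude only.

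What the reply does not remove is the rule itself. It is the only one the plan offers, and taken literally it drops a treatment failure. Section 9.4 continues follow-up as clinically indicated, but nothing says that the outcome enters the test.

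**Conclusion.** The gap is real and worth fixing before analysis; its expected effect is small. On the 20.1 rule an on-treatment progressor is replaced and absent from the primary recurrence test, and provided that progression is a failure, the test is biased toward success. The expected number is about 0.07 to 0.67 among 43, on an assumed 5% to 25% share. The matter deserves attention because the cutoff is only 4 or 5 failures.

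A reader might infer that the error rate is in fact above 0.20. The documents do not support that: without exclusions it is 0.099 to 0.180, and it passes 0.20 only at shares for which they give no evidence. A reader might also infer that patients with residual disease at restaging, or who recur later, are dropped. They are not: having completed treatment, they are evaluable.

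**What to change.** - State in 20.1 and 20.3.1.1 that the primary recurrence analysis includes every eligible patient who received at least one cetuximab dose.
- Count clinically confirmed progression or metastasis from first dose through two years after the end of treatment as failure, in addition to the events already listed.
- Use the same denominator in 20.2.
- Limit replacement to the paired-biopsy objective (20.3.2.1), and keep replaced patients in the recurrence analysis.
- State the pass cutoff for the number actually treated.
- Keep the completer analysis as a sensitivity analysis, and show best-case and worst-case handling of unknown two-year status the same way.

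Counting unknown status as failure in the primary analysis is not recommended. With 43 treated, P(X ≤ 5 − u | 43 − u, 0.0625) falls from 0.950 to 0.880, 0.747 and 0.540 for u = 1, 2 and 3 unknown.

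The cost is wording, plus two-year status for a few non-completers. That needs an explicit step, because 9.4 follows them only as clinically indicated and 17.2.4 takes a patient who starts another non-surgical therapy off study. The observed failure rate may be slightly less favourable. Power at 6.25% is 0.950 if 43 are treated, against 0.928 for 36 completers; it would be slightly below that for 39 to 42 completers (0.967 to 0.955).

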20.2 Early Stopping Rules for Toxicity or Lack of Efficacy

In UMCC 9921 and UMCC 2-21, 2/32=6% of patients similar to those who will be treated in the current trial did not achieve tumor control. An early stopping rule will only be feasible for the identification of probability of treatment failure much higher than that. Table 1 describes the stopping rule for failure to control, which was derived using the method due to Thall, Simon and Estey [31], implemented in M.D. Anderson program multc98. **Failure is defined as local-regional recurrence or metastasis, but not second primary cancer, nor microscopic disease found in elective neck dissection, nor PET findings without correlative clinical evidence of disease persistence or recurrence.** For each number of patients enrolled, if *at least* as many failures as stated occurs (e.g., 2/5), accrual will be stopped. The rule was constructed to stop the trial if the probability that the failure rate of the experimental therapy exceeded 0.1625 (0.1 more than the historical rate) is at least 0.75.

# Patients	# Failures
5	2
10	3
15	4
20	5
25	6
30	7

Table 1 Stopping rule for failure to control tumor

Because the trial will only be stopped early for failure, and the stopping rule does not constitute an interim analysis, there will be no adjustment to the p-values of the analyses in Section 20.4.

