Despite the favorable prognosis associated with, HPV-positive tumors, this biologic marker has not yet been used to determine therapeutic management. We postulate that there are two subsets of HPV-positive SCCOP patients; those who are cured by current therapies but may be suffering unnecessary morbidity from over-treatment and those who are at higher risk for disease progression and require more aggressive therapies. In prior work, we have investigated tobacco use and the HPV-16 biomarker as variables that can differentiate patients to one of those two subgroups, thereby allowing clinicians to safely develop more selective therapies for subsets of HPV-positive SCCOP patients.

One hundred and twenty-four patients with newly diagnosed, stage III or IV SCCOP whose tumors were analyzed for HPV presence and type were included in this study. Patients were treated according to one of two consecutive treatment protocols at the University of Michigan. Of the 124 patients, one hundred two were HPV-positive (82.3%) and 22 (17.7%) were HPV negative. Thirty- two (32/102, 32.4%) had disease progression (DM, LR, or SP). Seventeen patients (17/124, 13.7%) developed DMs (12 HPV-positive; 5 HPV-negative), nine (9/124; 7.3%) developed LRs (5 HPVpositive; 4 HPV-negative), and 8 (8/124; 6.5%) developed SPs (5 HPV-positive; 3 HPV-negative). Of thirty-three HPV-positive never-tobacco users, only one patient had disease progression (DM) (1/32, 3%), and an additional patient had a second primary in the oral cavity. Approximately two- thirds (68%) of the 102 HPV-positive patients were former or current tobacco users. Of these 69 patients, 18 (26%) developed a total of 20 disease progression events. All of the 22 HPV-negative SCCOP patients were tobacco users at some time. Twelve of the 22 (55%) HPV-negative former or current tobacco users had disease progression events (five DMs, four LRs, and three SPs). Sixteen

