4.0 INCLUSION CRITERIA

- 4.1 Patients must have pathologically-confirmed, previously untreated, stage III-IV(excluding N3 or T4) squamous cell carcinoma of the oropharynx, without evidence

of distant metastasis

4.2 Pretreatment tumor biopsy with sufficient tumor for HPV or p16 analysis is required. The tumor must be HPV(+) or p16(+)

4.3 Smoking history <10 pack-year or equivalent (including cigarettes, cigars, pipes, chewing tobacco, and/or marijuana.) One cannabis joint is equivalent to 5 cigarettes. (Aldington et al, Thorax 2007; 62:1058-1063)

Smoking status definitions (National Health Interview Survey and Behavioral Risk Factor Surveillance System (Nelson DE et al, Am J Pub Health 2003;93:1335):

- Smokers: smoking now every day or some days in past month
- Quitters: at least 100 cigarettes/lifetime and not smoking in the past 1-12 months
- Former smoker: at least 100 cigarettes/lifetime and not smoking >12 months
- Never smokers: <100 cigarettes (or equivalent)/lifetime

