20.4.2 Power of primary analysis endpoints

20.4.2.1 The ultimate goal of this research program is to conduct a randomized noninferiority trial to demonstrate that reducing the intensity of therapy in low-risk patients reduces the probability of toxicity while not increasing the probability of tumor recurrence. Such a trial will require hundreds of patients and will be possible only in the cooperative group setting. The purpose of this Phase II trial is to provide preliminary evidence that reduced intensity therapy is practical, and to provide initial evidence of efficacy and toxicity that can be used to design such a trial. The use of the relatively high significance level ($\alpha=0.2$) is not uncommon in early Phase II (e.g., Simon two-stage) trials with limited sample sizes. Out of 33 non-smoking HPV+ patients in the UMCC 2-21 reference set, three patients have died disease-free, and one patient has died from distant metastases. One additional patient in this group has developed a second primary tumor in the oral cavity. All other patients are alive and disease-free. Because the number of events is low, a time-to-event analysis is impractical, and analyses for sub-populations are also unlikely. Because the power will be modest even if the observed failure rates are 2-3 times the control rate, this trial will not definitively test that reduced intensity treatment is as effective as standard chemoradiation, but, if successful, will accrue sufficient data to motivate a true non-inferiority trial.

20.4.2 The power calculations for the toxicity endpoints (Primary Objective 2) will be represented by dysphagia, which is considered the most important. In UMCC 2-21, the patient-reported eating domain score of the HNQOL instrument increased from 10.5 ± 14.9 (mean \pm standard deviation) pre-RT to 25.7 ± 18.9 twelve months after treatment. Videofluoroscopy scores increased from 2.37 ± 1.35 pre-RT to

3.7 ± 1.18 twelve months after treatment. The power of the repeated measures analysis for Primary Objective 2 for these endpoints was assessed by Monte Carlo simulation as the mean twelve month value was reduced from the twelve-month level in UMCC 2-21 (0% decrease) to the baseline UMCC 2- 21 level (100% decrease).

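### The 2/32 (6%) benchmark behind the 0.1625 stopping threshold is not shown to describe the patients enrolled, and it appears to count an event that the rule itself excludes

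*Combined protocol and SAP*

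**What the plan says.** Section 20.2 takes its historical rate from UMCC 9921 and UMCC 2-21, where "2/32=6% of patients similar to those who will be treated in the current trial did not achieve tumor control". It does not define similar. Failure means local-regional recurrence or metastasis, and second primaries are expressly left out. Accrual stops when the probability that the failure rate "exceeded 0.1625 (0.1 more than the historical rate) is at least 0.75". Table 1 turns this into limits of 2/5, 3/10, 4/15, 5/20, 6/25 and 7/30: "For each number of patients enrolled, if *at least* as many failures as stated occurs (e.g., 2/5), accrual will be stopped". Table 2 (Section 20.4.1) gives stopping probabilities of 0.05 at a true rate of 0.06 and 0.59 at 0.2, with nothing in between.

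The likely source is the 124-patient stage III or IV series in Section 1.0, for which no T4 or N3 exclusion is mentioned. It reads "Of thirty-three HPV-positive never-tobacco users, only one patient had disease progression (DM) (1/32, 3" (per cent), adds one further patient with an oral-cavity second primary, and puts the never-users' risk of distant metastasis or second primary at 6%. For HPV-positive tobacco users it says: "Of these 69 patients, 18 (26%) developed a total of 20 disease progression events". Section 20.4.2.1 describes the reference differently, from one protocol and with another denominator: "Out of 33 non-smoking HPV+ patients in the UMCC 2-21 reference set", again with one death from metastasis and one second primary.

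Eligibility in Section 4.0 is "stage III-IV(excluding N3 or T4) squamous cell carcinoma of the oropharynx", with "Smoking history <10 pack-year or equivalent". Section 4.3 defines current smokers, quitters and former smokers and excludes none of them.

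**The concern.** The stopping threshold is the historical rate plus 0.10, so any error in that rate passes straight into it. The benchmark seems to differ from the trial in three respects: tobacco exposure (never-users against users under a cap), stage (no stated T4/N3 exclusion against both excluded) and the event counted (a second primary included against second primaries excluded).

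If the standard-therapy failure rate in eligible patients is above 6%, the rule could stop accrual although cetuximab-RT is no worse. If it is below 6%, the rule tolerates a larger excess of failures than the stated 0.10. The descriptive comparison with past experience is exposed in the same way: a difference in tobacco mix could be read as an effect of de-escalation.

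**Working it through.** **1. Reproduce the plan's figures.** The inputs are the Table 1 limits at looks of 5, 10, ..., 30 patients, with outcomes assumed known at each look. An exact binomial recursion carries the distribution of failures from look to look and removes the paths that reach a limit. It gives P(stop) = 0.046, 0.594, 0.912, 0.992 and 0.9997 at true rates 0.06, 0.2, 0.3, 0.4 and 0.5. Table 2 states 0.05, 0.59, 0.91, 0.99 and 0.99, so its stopping probabilities are right. The threshold is 2/32 + 0.10 = 0.0625 + 0.10 = 0.1625. With an assumed prior of mean 0.0625 and weight 2 (the plan states no prior), the smallest count with posterior probability of at least 0.75 reproduces all six limits.

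**2. Count failures as Section 20.2 defines them** (counts from Section 1.0).

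- HPV-positive patients: 12 distant metastases (DM), 5 local-regional recurrences (LR), 5 second primaries (SP).
- Never-users: 1 DM and 1 SP. Only the DM is a failure, so the rate is 1/33 = 0.030 or 1/32 = 0.031.
- Ever-users, by subtraction: 11 DM + 5 LR + 4 SP = 20 events in 18 patients. At most 4 of the 18 had only an SP, so at least 14 had LR or DM. LR and DM together number 16, so at most 16 did. The rate is 14/69 to 16/69 = 20% to 23%.

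For never-users the like-for-like threshold is 0.030 + 0.10 = 0.130 (0.131 with 1/32).

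**3. Fill the gap in Table 2.** Under the existing Table 1:

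| True failure rate | P(stop early) |
|---|---|
| 0.03 | 0.010 |
| 0.06 | 0.046 |
| 0.10 | 0.146 |
| 0.12 | 0.220 |
| 0.16 | 0.402 |
| 0.20 | 0.594 |

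**4. False stops with no treatment effect.** Assume a share f of enrolled patients are tobacco users with failure rate r, and the rest are never-users at 1/33: p = (1 − f)/33 + f·r. For example, f = 0.5 and r = 16/69 gives 0.0152 + 0.1159 = 0.131.

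| f | r = 1/33: p, P(stop) | r = 14/69: p, P(stop) | r = 16/69: p, P(stop) |
|---|---|---|---|
| 0.2 | 0.030, 0.010 | 0.065, 0.055 | 0.071, 0.066 |
| 0.3 | 0.030, 0.010 | 0.082, 0.093 | 0.091, 0.117 |
| 0.5 | 0.030, 0.010 | 0.117, 0.207 | 0.131, 0.267 |

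The columns with r = 14/69 and 16/69 are outer cases. The 69 used tobacco in any amount and carry no stated stage exclusion, and both features should put them above eligible users.

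**5. Effect on the limits.** With the same +0.10 margin and a prior of weight 2, a 3% benchmark gives 2/5, 3/10, 4/15, 5/20, 5/25, 6/30. A 10% benchmark gives 3/5, 4/10, 5/15, 6/20, 7/25, 8/30.

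**The case against.** The strongest reply is that the protocol does justify grouping light users with never-users. The recursive-partitioning analysis cited in Section 1.0 places HPV-positive patients with at most 10 pack-years, below T4 and below N3, in its low-risk class. Section 1.0 also calls the evidence on HPV and smoking conflicting. This has force against using the 69 ever-users as more than an outer bound. But that analysis classifies risk of death, the protocol quotes no recurrence rate from it, and Section 20.2 does not draw on it.

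Three further points stand. Section 20.2 does not name its source group, so the link to never-users is an inference from matching counts and from the 6% in Section 1.0. Table 2 is conditional on the true rate and extends well above 0.06, so the rule is not miscalculated. The primary test in Section 20.3.1.1 uses a fixed 0.20 and does not depend on 2/32.

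A reader might infer that 6% is simply too low and that the false-stop risk is several times the stated one. Taking 2/33 for never-users and 18/69 for users at f = 0.5 gives 0.5 × 0.061 + 0.5 × 0.261 = 0.161, and a stopping probability of about 0.40. The documents do not support this, because both inputs count second primaries, which the rule excludes. On the rule's definition the same mix gives at most 0.131 and 0.27, before any allowance for the pack-year cap or the stage exclusion.

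**Conclusion.** The benchmark is not shown to describe the enrolled patients, and it appears not to match the rule's own failure definition. The definitional mismatch is the firmer of the two: without the second primary, the never-user rate is about 3% rather than 6%, and the threshold about 0.13 rather than 0.1625. The population mismatch is real, but its net direction cannot be fixed from the documents, since tobacco exposure should raise the rate and the T4/N3 exclusion should lower it. It would go too far to say that the stated margin and false-stop rate are wrong for these patients.

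For an assumed user share of 20% to 50%, the false-stop risk with no treatment effect lies between about 0.01 (users behave like never-users) and about 0.27 (users behave like all ever-users), against the stated 0.05. This rests on the inferred source of 2/32, on the subtraction of events, and on outcomes being known at each look. The consequences are confined to the early stopping rule and the descriptive comparison with past experience.

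**What to change.** Re-tabulate the UMCC 9921 and 2-21 series for patients who meet Section 4.0 (HPV or p16 positive, within the pack-year limit, no T4, no N3), counting only local-regional recurrence or metastasis as Section 20.2 defines failure. Replace 2/32 with that count, then rederive 0.1625 and Tables 1 and 2 from it. Add Table 2 rows at 0.10, 0.12 and 0.16. Use one denominator and one source in Sections 20.2 and 20.4.2.1, which now give 32 from two protocols and 33 from one.

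If pack-years cannot be recovered, drop the claim of similarity from Section 20.2 and at least remove the second primary from the benchmark. Report the recurrence proportion in never-users beside the all-patient result, descriptively only, because Section 20.4.2.1 already regards sub-population analyses as unlikely with so few events.

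The cost is a re-tabulation of data the sponsor should already hold, a rerun of the multc98 program and a text edit; no extra patients are needed. The sponsor should accept in advance that the rule may move either way. Under the assumed prior, a 3% benchmark lowers the last two limits by one failure, and a 10% benchmark raises every limit by one. The stated false-stop rate may also look less favourable.
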